3.6 Proportion of Subjects with Age-Normal Stereoacuity at 36-Months

A treatment group comparison of the proportion of subjects meeting age-normal near stereoacuity at 36 months will be performed using Barnard's exact test.

Subjects are considered to have age-normal stereoacuity if their best reported near stereoacuity (*see section 3.5*) is within age-normal range.

3.7 Subgroup Analysis

In accordance with NIH guidelines, a subgroup analysis of treatment effect according to gender, as well as race/ethnicity, will be conducted. Binomial regression will be used evaluate if the difference between treatment groups in failure rate differs by subgroup. A model will be fit for

each factor of interest and will include the factor, treatment group, and an interaction term between the treatment group and the factor of interest.

Treatment effects in subgroups based on baseline factors will also be assessed. The subgroups of interest include baseline spherical equivalent anisometropia and baseline spherical equivalent refractive error. Failure status at 36 months post-randomization will be tabulated by subgroup and reviewed for consistency. The subgroup definitions for the planned subgroup analyses are as follows:

- Spherical equivalent anisometropia: <0.50D, 0.50D - <1.00D, 1.00D to 1.50D
- Spherical equivalent refractive error: +3.00D to <+4.00D, +4.00D to <+5.00D, 5.00D to 6.00D, $\geq 6.00D$

A Poisson regression using robust variance estimation will be used if the binomial regression model does not converge. If convergence issues are encountered when using the Poisson model, logistic regression will be used to make statistical inferences. For consistency, the same model will be used for all analyses. If the Poisson model is required for one of the analyses, the Poisson model will be used in all analyses.

4.0 Exploratory Analyses

Exploratory analyses will be performed separately for each primary cohort. Analyses will be considered statistically significant if the p-value is less than 0.01.

4.1 Presence of Amblyopia at 36 Months

The number and proportion of subjects in each treatment group that have amblyopia at the 36-month outcome will be calculated separately in each primary cohort. The best reported visual acuity in each eye (*see section 3.2*) will be used to calculate interocular difference (IOD). Amblyopia will be defined as ≥ 2 logMAR lines of IOD if visual acuity is 20/25 or worse in the better-seeing eye, and ≥ 3 logMAR lines of IOD if visual acuity is 20/20 or better in the better-seeing eye. A treatment group comparison of the proportion of subjects who developed amblyopia will be performed using a Barnard's exact test.

4.2 Binocular Near Visual Acuity at 36 Months

A treatment group comparison of near visual acuity at the 36-month outcome exam will be performed using an ANCOVA model, adjusting for age at the 36-month visit.

4.3 Change in Refractive Error from Baseline to Outcome

An analysis of covariance model will be used to compare the change in spherical equivalent (SE) refractive error in the eye that was more hyperopic at baseline from baseline to 36 months between treatment groups. The model will adjust for SE refractive error at baseline. The analysis will be repeated for the eye classified as less hyperopic at baseline.

If the change in refractive error differs at 36 months, an analysis of covariance model will be used to evaluate whether the relationship between the relationship between age at baseline and change in refraction from baseline to 36 months in the more hyperopic eye differs by treatment group. The model will include age at baseline, treatment group, and an interaction between age at baseline and treatment group. Analyses will be repeated to evaluate whether the relationship between age at baseline and change in refractive error from baseline to 36 months in the less hyperopic eye differs by treatment group.

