1 **Hyperopia Treatment Study (HTS1)**
 2 **Immediate versus Delayed Treatment In Children with Moderate**
 3 **Hyperopia**

4
 5 **Statistical Analysis Plan**
 6 **Version 3.0**

7
 8
 9
 10 Statistical Analysis Plan Version: 3.0, 25Jul18
 11 Protocol Version: 3.0, 28Jan15

12
 13
 14 **VERSION HISTORY**

The following table outlines changes for the analysis plan:

VERSION NUMBER	AUTHOR	APPROVER	EFFECTIVE DATE	REVISION DESCRIPTION*
1.0	[name]	[name]	12-19-17	Initial draft written after study was completed but before manuscript was written.
2.0*	[name]	[name]	05-14-18	Lead authors decided to redefine “best” stereoacuity and visual acuity at the 3-year outcome visit to be consistent with what was done for the IXT study. When preparing to unmask the study investigators to the results, the leads realized that it was not our intent to compare deterioration rates between the two groups. In the planning phase, the planning committee felt the deterioration rates in each group would aid in interpreting the results. The committee felt a formal statistical comparison was not needed because the rate of deterioration was expected to be higher in the observation group than in the glasses group.
3.0*	[name]	[name]	07-27-18	Lead authors decided to redefine best stereoacuity and best visual acuity at the 3-year outcome visit as the best of measurements reported with and without trial frames, during the initial assessment and retest, if required. During their final review of the manuscript, the leads realized that results reported for primary and secondary analyses were discordant. The leads determined that the definitions of best stereoacuity and best visual acuity needed updating to reflect the study design and to be in concordance with results reported in the primary analysis.

* indicate in the description if the changes were made after review of outcome data

15 **1.0 Primary Objective**

16 The primary study objective is to compare visual outcomes and development of strabismus after a
17 36-month follow-up period in two age cohorts (children age 12 to <36 months and children age
18 36 to <72 months) with moderate hyperopia (spherical equivalent +3.00D to +6.00D in either
19 eye) who are prescribed glasses either immediately or only after pre-specified deterioration
20 criteria are met.

21
22 **2.0 Primary Analysis**

23 The primary analysis will be a treatment group comparison of the proportion meeting failure

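### SAP section 4.3: the age-by-treatment model for refractive change omits the baseline refraction that the main model adjusts for, at some cost in precision

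*SAP*

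**What the plan says.** SAP section 4.3 has two steps, each done for the eye that was more hyperopic at baseline and repeated for the less hyperopic eye.

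- **Main comparison.** An ANCOVA compares the arms on change in SE from baseline to 36 months: "The model will adjust for SE refractive error at baseline".
- **Age-by-treatment model.** This is conditional: "If the change in refractive error differs at 36 months, an analysis of covariance model will be used" to examine whether age at baseline relates differently to refractive change in the two arms. "The model will include age at baseline, treatment group, and an interaction between age at baseline and treatment group".

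Section 4.0 sets the frame: "Exploratory analyses will be performed separately for each primary cohort", and "Analyses will be considered statistically significant if the p-value is less than 0.01". The cohorts, defined in section 1.0, are children aged 12 to <36 months and 36 to <72 months.

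**The concern.** Both models have the same outcome for the same eye. By adjusting the main model for baseline SE, the SAP treats that variable as worth adjusting for when change is analysed. There is good reason to: a change score contains its own baseline, and children are enrolled on the level of their refractive error, so regression toward the mean is plausible. The second model drops the covariate without comment.

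What is at stake is the precision of the age-by-arm coefficient. Interactions are usually estimated with less precision than main effects. Here each cohort is also analysed alone at a 0.01 threshold, so avoidable residual variance is unwelcome.

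A secondary matter is the gate. A test of the average effect is a weak screen for effect modification, because effects that run in opposite directions at different ages within a cohort can average out.

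**Working it through.** The SAP states no sample size, standard deviation, correlation or power for this analysis, so there is no figure of its own to reproduce.

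**1. Model terms side by side (SAP section 4.3)**

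| | Main model | Age-by-treatment model |
|---|---|---|
| Outcome | Change in SE, baseline to 36 months | Same |
| Treatment group | Yes | Yes |
| Baseline SE | Yes | Not listed |
| Age at baseline | Not listed | Yes |
| Age × treatment | No | Yes |

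**2. Bias.** The interaction coefficient is the difference between arms in the slope of change on age. If baseline SE is related to age and acts additively on change, omitting it shifts the age slope by the same expected amount in each arm, because arm is randomised. The shift cancels in the difference, so only precision is affected.

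**3. Precision.** Let *r* be the partial correlation of baseline SE with change, given age and arm. Adding baseline SE multiplies the residual SD, and so the interaction's standard error (SE*int*), by √(1 − *r*²), apart from one degree of freedom. Leaving it out is equivalent to needing 1/(1 − *r*²) times as many subjects. The values of *r* are assumptions.

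| *r* | √(1 − *r*²) | Cut in SE*int* | 1/(1 − *r*²) |
|---|---|---|---|
| 0.1 | 0.995 | 0.5% | 1.01 |
| 0.2 | 0.980 | 2.0% | 1.04 |
| 0.3 | 0.954 | 4.6% | 1.10 |
| 0.4 | 0.917 | 8.3% | 1.19 |
| 0.5 | 0.866 | 13.4% | 1.33 |
| 0.6 | 0.800 | 20.0% | 1.56 |

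At *r* = 0 nothing is lost.

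**4. What this means for power.** Simulation, 4,000 runs per scenario, two-sided alpha 0.01, age uniform within the cohort. The treatment effect is assumed to run from −1 SD at the youngest age to +1 SD at the oldest, averaging zero. There is no gate at this step. The arm sizes are also assumed.

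| *r* | 50 per arm: without → with baseline SE | 100 per arm: without → with |
|---|---|---|
| 0.2 | 0.59 → 0.61 | 0.92 → 0.93 |
| 0.4 | 0.58 → 0.67 | 0.92 → 0.96 |
| 0.6 | 0.58 → 0.82 | 0.92 → 0.99 |

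**5. The gate.** Same simulation, with the main test at 0.01 required first.

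- *Average effect zero (full reversal within the cohort).* The main test passes in about 1% of runs, which is its alpha. The SAP's sequence then detects the interaction in 0.004 to 0.010 of runs.
- *Average effect 0.5 SD.* The SAP's sequence detects it in 0.26 to 0.37 of runs at 50 per arm and 0.74 to 0.87 at 100 per arm. The gated model with baseline SE added gives 0.26 to 0.51 and 0.75 to 0.93. The adjusted, ungated model gives 0.60 to 0.82 and 0.94 to 0.99.

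The loss from the gate is therefore near total only when the effects nearly cancel, and otherwise depends on the average effect and the sample size.

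**The case against.** **The list may not be exhaustive.** One could read the second model as inheriting the baseline adjustment from the paragraph's first model. The SAP does not say so. If that was the intent, the same one-sentence change settles it.

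**Bias, or conflicting adjusted effects.** A reader might infer that the two models give incompatible answers or that the interaction is biased. The documents do not support that. The models address different questions, an average difference and a difference in slopes, and with randomised arms and an additive baseline effect the omission costs precision only. This objection stands.

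**The size is unknown.** It is tempting to quote only the upper part of the range. Nothing in the SAP fixes the correlation. Enrolment is confined to +3.00D to +6.00D in either eye, which restricts the spread of baseline SE and tends to lower the correlation. A fair range has to start near zero, where the gain is trivial. This also stands.

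**The gate is a legitimate choice.** Looking for variation by age only after an effect is seen is a common way to limit exploratory tests. A reader might infer that the gate hides whatever the interaction looks for. It does not: an effect of varying size in one direction can pass. Because the cohorts are analysed separately, opposite effects in younger and older children would show in the two main comparisons. Only a near-cancelling reversal inside one cohort is reliably hidden. On the other side, section 3.7 plans interaction models for gender and race/ethnicity without any such condition, so the gate is not the SAP's general practice. It remains a choice rather than an error.

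**Conclusion.** The covariate point holds. Within one section, the same change score is adjusted for baseline SE in the main model and not in the age-by-treatment model, with no reason given. The cost is precision of unknown size: the interaction's standard error would fall by about 0.5% to 20% if the partial correlation lies between 0.1 and 0.6, an assumed range, and not at all if it is zero.

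Removing the gate is optional. The near-total loss of detection in the simulation needs an assumed full reversal within one cohort, and no effect size or sample size in the SAP supports that particular scenario.

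This is a minor point. The analysis is exploratory, and nothing here bears on the failure comparison in section 2 or on the secondary analyses in section 3.

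**What to change.** **Recommended.** In section 4.3, add baseline SE refractive error of the same eye to the terms of the age-by-treatment model, for the more hyperopic eye and again for the less hyperopic eye. This takes one sentence and one degree of freedom per model, and uses a variable the main model already requires.

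**Optional.** State that the interaction model is fitted whatever the result of the main comparison. The cost is up to four more exploratory tests (two eyes × two cohorts), each judged at 0.01. If the gate is kept, say what "If the change in refractive error differs at 36 months" means: presumably p < 0.01 under section 4.0, and whether each eye's result opens only that eye's model.

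The version history dates the first version of the SAP after study completion and the current one to the final manuscript review. Any change made now, or any re-analysis, should therefore be labelled post hoc.

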4.4 Factors Predictive of Failure and 36-Month Visual Outcomes

The following characteristics will be evaluated as potential predictors of failure rate, mean best reported distance visual acuity (logMAR), best reported stereoacuity (log arcsecond), and measureable heterotropia; all assessed at the 36-month examination, or 37-month exam if required:

- Accommodative response at baseline
- Family history of amblyopia or strabismus at baseline
- Use of ADHD medication at any time before the 36-month visit

For this analysis, the accommodative response will be defined as a composite of the lens power and the retinoscopy. Eyes for which the reflex is classified as “with motion” will maintain a positive lens power, and a negative lens will be converted to a negative value if the reflex is classified as “against motion”. If the reflex is “neutral”, a value of 0 will be imputed for the lens power.

Linear regression will be used to evaluate accommodative response as a predictor of mean best distance visual acuity and of best near stereoacuity. AN(C)OVA models will be used to evaluate family history of amblyopia or strabismus and use of ADHD medication as predictors of mean best distance visual acuity and of best near stereoacuity. Logistic regression will be used to evaluate each baseline characteristic as a predictor of failure rate and measureable heterotropia. Each model will evaluate the relationship between one potential predictor and one dependent variable.

Seeing as the study aims to obtain the best outcome for each subject, subjects will be classified as having measureable heterotropia if all reported results indicate that measureable heterotropia is present. If any of the required assessments indicate that measureable heterotropia is not present, the subject will not be classified as having measureable heterotropia.

5.0 General Principles for Analysis

5.1 Classifying Visits

The analysis visit window for the randomized clinical trial will be as follows:

1. 6-month – >3.5 to 9 months (106 to 274 days) after randomization
2. 12-month – >9 to 15 months (275 to 456 days) after randomization
3. 18-month – >15 to 21 months (457 to 639 days) after randomization
4. 24-month – >21 to 27 months (640 to 822 days) after randomization
5. 30-month – >27 to 33 months (823 to 1004 days) after randomization
6. 36-month – >33 to 42 months (1005 to 1282 days) after randomization

A visit will be considered missed if it is completed out of window or not completed, but a later visit is completed. There is no analysis window for the 37-month visit. Data from the 37-month visit will be used in analysis if the visit is completed.
